### 11.3.1.7 Endoscopic improvement and endoscopic remission

**Endoscopic improvement** is achieved if the Mayo central endoscopic sub-score is 0 or 1.

**Endoscopic remission** is defined as Mayo central endoscopic sub-score = 0.

Endoscopic improvement and remission (central reading sub-score) will be presented as proportion of patients (n and percentage) (*Table 14.2.6.1 and 14.2.6.2*).

### 11.3.1.8 Sustained clinical remission and sustained endoscopic remission/improvement

**Sustained clinical remission** is defined as clinical remission at the given timepoint (M12, M24, M36 or M48) with clinical remission at BOLS.

**Sustained endoscopic improvement** is defined as endoscopic improvement at the given timepoint (M12, M24, M36 or M48) with endoscopic improvement at BOLS.

**Sustained endoscopic remission** is defined as endoscopic remission at the given timepoint (M12, M24, M36 or M48) with endoscopic remission at BOLS.

Sustained clinical remission and sustained endoscopic improvement/remission will be presented as proportion of patients (n and percentage) (*Table 14.2.7.1 and 14.2.7.2*).

#### 11.4 PK ANALYSES

Not applicable.

#### 11.5 PD ANALYSES

Not applicable.

#### 11.6 SAFETY ANALYSES

Analysis of safety will be performed on the safety dataset consisting in all patients who received at least one dose of ABX464 in the study. In safety tables of continuous variables, standard descriptive statistics (n, mean, SD, SEM, median, minimum and maximum) will be presented.

##### 11.6.1 Adverse Events

All adverse events (AE) will be classified using the latest version of the MedDRA coding dictionary down to the lower level term.

Events will be classified as treatment-emergent if they started or increased in severity on or after the first date of medication dosing and up to study closure or withdrawal date. If an event start date is partial, then the start day, month, year or stop date will be used to determine if the event is treatment-emergent. If the classification of the AE cannot be determined from the data available, then the event will be considered treatment-emergent.

##### **Adverse Events of Special Interest (AESI):**

The following events will be considered as AESIs:

- Skin Lesions (regardless of its severity)
- Headaches (if lasts more than 72 hours AND is not resolved by standard painkillers)
- Anemia (Hemoglobin drop  $> 2$  g/dL from baseline or Hemoglobin  $< 8$  g/dL)
- Hepatic enzymes (specifically, an increase  $\geq 3.0 \times$  ULN in liver transaminases (AST/SGOT and/or ALT/SGPT) or an increase  $\geq 2.0 \times$  ULN in total bilirubin without initial findings of cholestasis (elevated alkaline phosphatase))
- Severe (grade  $\geq 3$ ) infections and opportunistic infections
- Acute pancreatic adverse events (an elevation of serum lipase and/or amylase at least three times greater than the upper limit of normal will be reported as AESI)
- Malignancies including Non-Melanoma Skin Cancers
- Cardiac AESIs: any AE with the SOC “cardiac disorders” (Aortic valve disease, Asystole, Atrial fibrillation, Atrial flutter, 3rd degree AV block (AV block complete), Cardiac arrest, Chest pain – cardiac, Heart failure, Left ventricular systolic dysfunction, Mitral valve disease, Mobitz (type) II atrioventricular block (type 2, 2nd degree AV block), Myocardial infarction, Myocarditis, Pericardial effusion, Pericardial tamponade, Pericarditis, Pulmonary valve disease, Restrictive cardiomyopathy, Right ventricular dysfunction, Sick sinus syndrome, Tricuspid valve disease, Ventricular fibrillation, Ventricular tachycardia).

Further definitions for the AESIs are described in protocol section 8.2.

Two periods will be defined for TEAE:

- Any adverse event which occurs or worsens from first dosing (BOLS) to the last dosing day;
- Any adverse event which occurs after the last dosing day.

Adverse events will be described by primary system organ class and preferred term. Numbers and percentage of subjects, and number of occurrences of adverse event will be presented for:

- AE (*Table 14.3.1.1*);
- AE by severity (*Table 14.3.1.2*);
- TEAE by relationship to study drug (*Table 14.3.1.3*);
- TEAE leading to investigational product discontinuation (*Table 14.3.1.4*);
- TEAE (*Table 14.3.1.5*);
- TEAE by severity (*Table 14.3.1.6*);
- Severe TEAE (grade 3 or 4) by relationship to study drug (*Table 14.3.1.7*);
- Serious TEAE (*Table 14.3.1.8*);
- TEAE of special interest (*Table 14.3.1.9*);

All adverse events will be listed and the data will be tabulated by body system/organ class (N and percentage).

If a patient has multiple AEs with the same preferred term, these will be summarised once within the count for n (%) of patients, but each event will be counted within the number of reports n of each AE. Changes in severity of the same AE (if collected) will be counted only once within the number of reports n of each AE.

The following will be presented in listing format within the data summaries:

- Deaths (*Table 14.3.2.1*);
- Serious Adverse Events (*Table 14.3.2.2*);
- Adverse Events which Led to Withdrawal (*Table 14.3.2.3*).

Further definitions and procedures regarding adverse events are stated in the protocol (Section 8).

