During non-clinical studies, the main clinical signs observed in non-clinical studies for ABX464 consisted of, ptalism and bodyweight loss which was dose proportional and severe in some cases. the main target organs affected were the gastro-intestinal tract and liver with the main macroscopic findings observed as dark foci in the glandular mucosa of stomach, adverse altered cell foci and bile duct hyperplasia in the liver, adverse erosion/ulcer in the forestomach, centrilobular hepatocellular degeneration/necrosis and liver necrosis. Some degree of anemia was found in the 9-month marmoset study with ABX464-N-Glu. Immunosuppression has been observed in a 9-month study with direct dosing of ABX464-N-Glu in cynomolgus monkeys. Two cases of cardiac fibrosis, likely associated with the Marmoset Wasting Syndrome, have been observed in a 9-month study with marmoset monkeys exposed to high doses of ABX464-N-Glu.

As of 30 November 2021, 1023 subjects have received ABX464, according to various administration schedules, in all completed, and ongoing open-label clinical studies across all indications. Out of these 1023 subjects, 830 subjects have been dosed with ABX464 50mg once daily (od) including 240 subjects for longer than 6 months with 197 for more than a year. In addition, 36 subjects have received ABX464 or placebo in the ongoing blinded clinical study (ABX464-921). All doses tested were well tolerated. 38 Serious Adverse Events were reported in all clinical studies, except COVID study (ABX464-401) which are reported separately in this IB. No fatalities were reported in non-COVID indication/population except one fatal case that was a road traffic accident and was unrelated to the study drug.

Anticipated ABX464 adverse events (regardless of their severity)

Frequent gastrointestinal symptoms such as abdominal pain, nausea, vomiting and diarrhea, as well as headaches, are described effects for ABX464, which are dose-dependent, with intensity going from mild to severe, occurring after treatment onset.

Therefore, designated anticipated AEs are:

- Headache
- Nausea
- Vomiting
- Abdominal pain (abdominal pain or upper abdominal pain)
- Diarrhea
- Back pain

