2.4. Secondary Endpoints

The secondary endpoints of this study are:

- The change from Day 0 in Total Mayo Score.
- The change from Day 0 in Partial Mayo Score.
- The time to UC worsening.
- The change from Day 0 in fecal calprotectin, CRP levels and ESR.
- The scores and changes from Day 0 in SF-36 Questionnaire scores.
- The miR-124 expression at month 12, month 36 and month 48.
- The number of incidences of treatment-emergent serious adverse events.
- The number of incidences of treatment-emergent adverse events of special interest.
- The number of incidences of adverse events leading to investigational product discontinuation.
- The number of incidences of specific laboratory abnormalities.
- Percentage of subjects reaching clinical remission at M12, M36, and M48.
- Percentage of subjects reaching clinical response at M12, M36, and M48.
- Percentage of subjects reaching endoscopic improvement at M12, M36, and M48.
- Percentage of subjects reaching endoscopic remission at M12, M36, and M48.
- Percentage of subjects reaching corticosteroid-free clinical remission at M12, M36, and M48.

The echocardiography secondary endpoints^[9] are:

- Absolute (%) change-from-previous echocardiogram of Left ventricle Ejection Fraction (LVEF) as measured by 2-dimensional echocardiography
- Number of subjects with a clinically relevant reduction (change-from-previous echocardiogram) of LVEF, defined as by > 10% reduction (absolute percentage points) to a value < 50%

- Absolute (%) change in Global Longitudinal Strain (GLS) from-previous echocardiogram
- Number of subjects with a relative percentage reduction in GLS by > 15% from the previous value
- Number of subjects with a reduction of LVEF > 10% (absolute percentage points) to a value $\geq 50\%$ with an accompanying fall in GLS > 15%
- Number of subjects with reduction in LVEF by > 10% (absolute percentage points) to a value $\geq 50\%$
- Changes from previous echocardiography of other echocardiographic parameters as described in a standard protocol, including 2-dimensional volumes, RV size and systolic function and valve function.

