Despite a lack/paucity of reported events in non-clinical and clinical trials, a potential impact on both innate and adaptive immune responses and the novel mechanism of action, could be a concern with regards to malignancies, mainly in the long-term. Therefore, all malignancies including non-melanoma skin cancers will be reported as an AESI.

Cardiac Fibrosis:

Two cases of cardiac fibrosis, likely associated with the marmoset wasting syndrome^[11], have been observed in a 9-month study with marmoset monkeys exposed to high doses of ABX464-N-Glucuronide. These findings were considered to be spontaneous. A review of the safety database for ABX464 has revealed no changes in troponin level compared with placebo or any increased reporting of cardiovascular adverse events compared with placebo. However, the following cardiac monitoring will be performed in this study:

Additional cardiac Laboratory monitoring procedures will include:

1. Monitoring of AST, Troponin and creatinine phosphokinase (CPK) blood levels at each study visit, including baseline visit plus the End of Study Visit
2. Monitoring of N-terminal pro b-type natriuretic peptide (NT-proBNP) blood levels every 6 months plus at the End of Study Visit.

A relative change of more than 20% from baseline values in cardiac laboratory parameters will be reported as an AESI.

Two-dimensional echocardiography with local evaluation will be performed every 6 months.

An independent Cardiovascular Safety Committee (ICVSC) will evaluate cardiac AESIs, treatment emergent echocardiographic findings, and treatment emergent changes of cardiac safety biomarkers (as detailed above).

The following treatment emergent adverse events (TEAEs) will also be categorized as Cardiac AESI:

Under the Cardiac SOC:

- Aortic valve disease
- Asystole

- Atrial fibrillation
- Atrial flutter
- 3rd degree AV block (AV block complete)
- Cardiac arrest
- Chest pain – cardiac
- Heart failure
- Left ventricular systolic dysfunction
- Mitral valve disease
- Mobitz (type) II atrioventricular block (type 2, 2nd degree AV block)
- Myocardial infarction
- Myocarditis
- Pericardial effusion
- Pericardial tamponade
- Pericarditis
- Pulmonary valve disease
- Restrictive cardiomyopathy
- Right ventricular dysfunction
- Sick sinus syndrome
- Tricuspid valve disease
- Ventricular fibrillation
- Ventricular tachycardia

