## Endoscopic Remission

| Visit   | n | xx         | xx         | xx         |
|---------|---|------------|------------|------------|
| Yes     |   | xx (xx.x%) | xx (xx.x%) | xx (xx.x%) |
| No      |   | xx (xx.x%) | xx (xx.x%) | xx (xx.x%) |
| Missing |   | xx (xx.x%) | xx (xx.x%) | xx (xx.x%) |

Etc

The denominator for each percentage is the number of patients within the column.

Endoscopic Improvement and Endoscopic Remission are based on central reading endoscopy.

Source: Listing 16.2.6.1

Path\Filename

Page x/y

Programming Note: Please present subgroups in the following order:

- All patients

Version Date 20 MAY 2021

Template STATt004

Page 51 of 97

- *Patients being in clinical response at Baseline Open-Label Study (BOLS)*
- *Patients not being in clinical response at Baseline Open-Label Study (BOLS)*
- *Patients previously treated with biological drugs*
- *Patients naive from biological drugs*

This layout also applies to:

*Table 14.2.6.2 Proportion of Patients: Endoscopic Improvement and Endoscopic Remission (NRI Set)*

*Table 14.2.7.1 Proportion of Patients: Sustained clinical remission and sustained endoscopic remission/improvement (OC Set)*

*Table 14.2.7.2 Proportion of Patients: Sustained clinical remission and sustained endoscopic remission/improvement (NRI Set)*

ABX464-102

ddMMMyyyy HH:MM

Period X

Table 14.3.1.1 Adverse Events (OC Set)

|  | 50mg ABX464 (101) + | Placebo (101) +   | Total
(N=xx) |
|--|---------------------|-------------------|-----------------|
|  | 50mg ABX464 (102)   | 50mg ABX464 (102) |                 |
|  | (N=xx)              | (N=xx)            |                 |
|  | E n (%)             | E n (%)           | E n (%)         |
| Any Adverse Event  | xx xx (xx.x%)       | xx xx (xx.x%)     | xx xx (xx.x%)   |
| Any Treatment-Emergent Adverse Event                     | xx xx (xx.x%)       | xx xx (xx.x%)     | xx xx (xx.x%)   |
| Any Serious Adverse Event                                | xx xx (xx.x%)       | xx xx (xx.x%)     | xx xx (xx.x%)   |
| Any Severe Adverse Event                                 | xx xx (xx.x%)       | xx xx (xx.x%)     | xx xx (xx.x%)   |
| Any Adverse Event leading to death                       | xx xx (xx.x%)       | xx xx (xx.x%)     | xx xx (xx.x%)   |
| Any Treatment-Emergent Adverse Event of Special Interest | xx xx (xx.x%)       | xx xx (xx.x%)     | xx xx (xx.x%)   |

The table presents number of events (E) and number and percentage of patients (n(%)).

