The denominator for each percentage is the number of patients within the column.

MedDRA version <XX.X>.

Period 1: Any adverse event which occurs or worsens from first dosing to the last dosing day. Period 2: Any adverse event which occurs after the last dosing day.

Source: Listing 16.2.7

Path\Filename

Page x/y

*Programming Note: Please present for both periods with the number of the period in the header (Period X).*

*This layout also applies to:*

*Table 14.3.1.4 Treatment-Emergent Adverse Events Leading to Investigational Product Discontinuation (OC Set)*

*Table 14.3.1.5 Treatment-Emergent Adverse Events (OC Set)*

Version Date 20 MAY 2021

Template STATt004

Page 53 of 97

*Table 14.3.1.7 Serious Treatment-Emergent Adverse Events (OC Set)*  
*Table 14.3.1.9 Treatment-Emergent Adverse Events of Special Interest (OC Set)*

ABX464-102

ddMMMyyyy HH:MM

Period X

Table 14.3.1.2 Adverse Events by Severity (OC Set)

| Severity           | 50mg ABX464 (101) +           | Placebo (101) +                                 | Total
(N=xx)                                 |
|--------------------|-------------------------------|---|---|
|                    | 50mg ABX464 (102)             | 50mg ABX464 (102)                               |   |
|                    | (N=xx)                        | (N=xx)  |   |
| E                  | n (%)                         | E   | n (%)   |
| Any Adverse Events | xx xx (xx.x%)                 | xx xx (xx.x%)                                   | xx xx (xx.x%)                                   |
| SOC                | Grade 1
Grade 3            | xx xx (xx.x%)
xx xx (xx.x%)                  | xx xx (xx.x%)
xx xx (xx.x%)                  |
| PT                 | Grade 1
Grade 1
Grade 3 | xx xx (xx.x%)
xx xx (xx.x%)
xx xx (xx.x%) | xx xx (xx.x%)
xx xx (xx.x%)
xx xx (xx.x%) |
| Etc                |                               |   |   |
| Etc                |                               |   |   |

The table presents number of events (E) and number and percentage of patients (n(%)).

The denominator for each percentage is the number of patients within the column.

MedDRA version <XX.X>.

Period 1: Any adverse event which occurs or worsens from first dosing to the last dosing day. Period 2: Any adverse event which occurs after the last dosing day.

Source: Listing 16.2.7

Path\filename

Page x/y

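### No planned summary table counts patients per AESI category, so risks that span several preferred terms have no single patient figure

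*SAP*

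**What the plan says.** Protocol 2.4 makes two related items secondary endpoints: "The number of incidences of treatment-emergent adverse events of special interest" and "The number of incidences of specific laboratory abnormalities". Neither document asks for a count per AESI category.

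SAP 11.6.1 lists eight AESI categories: skin lesions, persistent headache, anaemia, hepatic enzymes, severe or opportunistic infections, pancreatic events, malignancies and cardiac events. For the tables it then states "Adverse events will be described by primary system organ class and preferred term". On patient counts it says "If a patient has multiple AEs with the same preferred term, these will be summarised once within the count for n (%) of patients". It gives no counting rule for a group of terms.

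In SAP 15, the shell for Table 14.3.1.1 shows only overall rows. One of them pools all AESIs: "Any Treatment-Emergent Adverse Event of Special Interest". The same layout is assigned to "Table 14.3.1.9 Treatment-Emergent Adverse Events of Special Interest (OC Set". The adverse event listing shell (16.2.7) has no AESI flag or category column.

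For cardiac AESIs the SAP uses the cardiac disorders system organ class (SOC), with a list of terms. Protocol 8.2 has that list too, but it also makes a relative change of more than 20% from baseline in a cardiac laboratory parameter an AESI. The parameters are set out under "Monitoring of AST, Troponin and creatinine phosphokinase (CPK) blood levels at each study visit", with NT-proBNP added in the next item.

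**The concern.** Most AESI categories are composites. The hepatic category is met through AST, ALT or bilirubin, and the pancreatic one through lipase or amylase. Skin lesions and infections can each be coded to many terms. A reader of a long-term safety report wants to know how many of the 22 patients had each monitored harm. The plan instead offers one pooled figure, which adds skin lesions of any severity to malignancy and heart failure, and rows for single terms, which cannot be added up to patients. AST complicates this further, because under protocol 8.2 it belongs both to the hepatic criterion and to the cardiac-marker criterion. What is at stake is whether the report contains a pre-specified patient count for each risk that the protocol chose to monitor.

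**Working it through.** The plan states no figure to reproduce; protocol 9.4 gives sample size as not applicable. The check has three parts.

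**1. How far the term rows fix a category count.**

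Inputs:
- N = 15 + 7 = 22 patients enrolled (protocol 1.3). All are assumed to have been dosed.
- Patients are de-duplicated within a preferred term only (SAP 11.6.1).
- The term counts below are illustrative. They are not in the documents.

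For a category made of terms reported in n1, n2, ... patients:

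max(n1, n2, ...) ≤ distinct patients ≤ min(N, n1 + n2 + ...)

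| Term counts | Lower bound | Upper bound | Share of 22 |
|---|---|---|---|
| 2, 2 | 2 | 4 | 9.1% to 18.2% |
| 2, 2, 1 | 2 | 5 | 9.1% to 22.7% |
| 1, 1, 1, 1 | 1 | 4 | 4.5% to 18.2% |

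Take the first row as ALT increased in 2 patients and AST increased in 2. ALT is not a cardiac parameter, so the two ALT patients fix the hepatic minimum at 2. If one or both AST events were reported under the cardiac-marker criterion alone, the upper bound can fall but the lower bound cannot.

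Event counts behave differently. Each event is counted separately, so events do add across term rows.

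**2. Which categories are affected.**
- *Hepatic, pancreatic, skin lesions:* several terms, so patient counts are only bounded.
- *Severe or opportunistic infections:* several terms. A single SOC row would serve only if every such event codes to one SOC. The SAP does not define the category that way.
- *Cardiac:* the SAP ties this to one SOC, so the SOC row gives the SAP-defined count, assuming SOC rows count each patient once. The protocol's change of more than 20% in a marker falls outside that definition. Terms such as AST increased would not be expected under the cardiac SOC (a coding assumption).

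**3. Whether the laboratory outputs supply the counts (SAP 11.6.2 and 15).**
- The shift tables classify results as normal, abnormal clinically significant or abnormal not clinically significant. They apply none of the AESI thresholds.
- Table 14.3.3.5 lists abnormal values by patient with the reference range, so hepatic and pancreatic criteria in multiples of the upper limit of normal can be counted by hand.
- A haemoglobin fall of more than 2 g/dL, or a marker change of more than 20%, can occur within the normal range and so need not appear in Table 14.3.3.5. The full listings (16.2.8.1 and 16.2.8.2) hold the values, but as listings and not as a planned count.

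**The case against.** The strongest reply is that nothing required is missing. The endpoint is the overall number of AESIs, and the plan tabulates it as both events and patients. A reader might infer from the missing category rows that the AESI endpoint is not analysed; the documents do not support that.

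A reader might also infer that no monitored risk can be recovered from any table. That goes too far as well. The SAP-defined cardiac count has its SOC row, event counts add across terms, and threshold-based hepatic and pancreatic cases can be counted by hand among 22 patients. Of the six anticipated events in protocol 1.2.5, five (headache, nausea, vomiting, diarrhoea, back pain) should each be readable from one term row, if each codes to one term. Only "Abdominal pain (abdominal pain or upper abdominal pain" is a union of terms, and it stands in the introduction, where no objective, endpoint or analysis depends on it. Nor do the documents show that splitting by term will make harms look rarer, since every event is also listed.

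Finally, SAP 15 lets the programmer alter layouts for completeness and clarity, and shell rows may have been lost when the text was extracted.

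All of this limits the point without removing it. The SOC and preferred-term rule and the de-duplication rule are in the SAP text and do not depend on the shell. Permission to change a layout is not a specification of category rows. A hand count from listings is not a pre-specified summary, and Table 14.3.3.5 does not cover within-range changes.

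**Conclusion.** The point holds as a gap in the summary analysis. No planned summary table gives patients per AESI category, and for categories spanning several terms the patient count is only bounded. With two terms at 2 patients each of 22, the range is 2 to 4 patients, 9.1% to 18.2%; for any two terms with equal counts whose sum does not exceed N, the upper bound is twice the lower. The protocol's cardiac-marker criterion is a separate gap, because the SAP's cardiac definition does not include it although the SAP refers to protocol 8.2 for further definitions.

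This rests on the SAP text and the shells as they can be read, on illustrative term counts, and on the usual coding of laboratory terms outside the cardiac SOC. It does not affect the overall AESI count or any design figure. It is a cheap improvement that serves the primary safety objective directly.

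**What to change.** - In Table 14.3.1.9, make the eight AESI categories of SAP 11.6.1 the first-level rows, with events (E) and patients n (%), each patient counted once per category, and SOC and preferred term beneath.
- Add an AESI category variable to the analysis dataset and to Listing 16.2.7. Take it from the AESI form if the form records it (the documents do not show whether it does). Otherwise assign it at the data review meeting before database lock. Allow an AST event to be hepatic, cardiac or both.
- Reconcile the cardiac AESI definition in SAP 11.6.1 with protocol 8.2, so that it is clear how events reported under the marker criterion are counted.
- Optional: a grouped row in Table 14.3.1.5 that counts abdominal pain and upper abdominal pain together.

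The cost is SAP wording, one revised shell, a little programming and, if the form lacks the category, a short assignment exercise before lock. No additional patient assessments are needed.

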1.2.5. Previous clinical experience with ABX464

The effect of ABX464 in humans has been assessed in eighteen clinical trials:

- Completed clinical studies in healthy volunteers (ABX464-001, ABX464-002, ABX464-901, ABX464-902, and ABX464-903) and controlled studies in patients with ulcerative colitis (ABX464-101 and ABX464-103), in patients with rheumatoid arthritis (ABX464-301), in HIV infected subjects (ABX464-003, ABX464-004, and ABX464-005), and in COVID-19 infected patients (ABX464-401).
- Open label studies in ulcerative colitis (ABX464-102, ABX464-104, and ABX464-108) and rheumatoid arthritis (ABX464-302).
- A drug product formulation study (ABX464-905) is ongoing in Healthy Volunteers
- A bioequivalence study (ABX464-921) is ongoing in Japanese Healthy Volunteers.

As of 30 November 2021, 1023 subjects have received ABX464, according to various administration schedules, in all completed, and ongoing open-label clinical studies across all indications. Out of these 1023 subjects, 830 subjects have been dosed with ABX464 50mg once daily (od) including 240 subjects for longer than 6 months with 197 for more than a year. In addition, 36 subjects have received ABX464 or placebo in ongoing blinded clinical study (ABX464-921). Fourteen patients have received ABX464 50mg od for more than 3 years in the UC open label maintenance study (ABX464-102) and 248 patients have received ABX464 50mg for more than 6 months.

ABX464 was rapidly absorbed in healthy volunteers, HIV and UC patients with a Cmax observed approximately 1.5 to 2.9 hours after dosing. Exposure to ABX464 was comparable in all subjects receiving ABX464 at a given dose. PK of ABX464 were linear in the dose range 50-150mg. After repeated administrations of ABX464, an initial decrease in ABX464 AUC was observed and steady state was reached after 4 weeks of treatment.

ABX464 was rapidly metabolised to ABX464-N-Glu. ABX464-N-Glu had a much longer half-life compared to ABX464 (about 100 hours) largely contributing to the high exposures observed.

Food increased ABX464 exposure at least 2.8-fold while exposure to the metabolite was comparable in fed or fasted conditions.

Clinical Efficacy

Completed and ongoing studies with ABX464 in UC are:

- Phase 2a program with an 8-week induction (ABX464-101; completed) and a 4-year maintenance (ABX464-102; ongoing; 52-week interim analysis completed) studies

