2.3. Primary Endpoint

The primary endpoint of this study is defined as the number of incidences of treatment-emergent adverse events in the ABX464 treated subjects.

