## 2 STUDY OBJECTIVES

### 2.1 PRIMARY OBJECTIVE

The primary objective of the study is to evaluate the long-term safety of ABX464 given at 50 mg once daily in subjects with Moderate to Severe Active Ulcerative Colitis.

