## 4 STUDY VARIABLES

### 4.1 PRIMARY VARIABLE

The primary endpoint of this study is defined as the number of incidences of treatment-emergent adverse events in the ABX464 treated subjects.

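### The adverse event tables for the long-term safety objective give only event counts and crude percentages, with no link to time at risk, although follow-up runs from about 1 to 48 months

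*SAP*

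**What the plan says.** SAP 2.1 states: "The primary objective of the study is to evaluate the long-term safety of ABX464 given at 50 mg once daily". Protocol 2.3 defines the primary endpoint as the "number of incidences of treatment-emergent adverse events in the ABX464 treated subjects", and SAP 4.1 repeats this.

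SAP 11.6.1 specifies the AE summaries: "Numbers and percentage of subjects, and number of occurrences of adverse event will be presented for" a list that includes all treatment-emergent AEs (TEAEs), serious TEAEs, TEAEs leading to discontinuation and TEAEs of special interest. The shells in SAP Section 15, from Table 14.3.1.1 on, show events (E) and patients as n (%). Their footnote reads: "The denominator for each percentage is the number of patients within the column".

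The only time split is into two periods. Period 1 is defined as "Any adverse event which occurs or worsens from first dosing (BOLS) to the last dosing day"; Period 2 is everything after the last dose.

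SAP 5.1 derives treatment exposure per patient as last dose date minus first dose date plus 1. SAP 11.7 summarises it in Table 14.3.7, in the same three columns as the AE tables. No AE table uses it. Neither document plans a rate per patient-year, a time-to-first-event or cumulative-incidence estimate, AE tables by time interval, or a confidence interval for AE percentages.

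On follow-up, Protocol 3.1.1 plans 48 months of treatment. Protocol 1.3 reports 22 enrolled, with three not reaching the Month 12 set: one withdrew at Month 1, one had a headache at Month 4, and one was lost to follow-up at an unstated time. Protocol 1.2.5 adds, as of 30 November 2021: "Fourteen patients have received ABX464 50mg od for more than 3 years in the UC open label maintenance study (ABX464-102".

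**The concern.** A patient who left at Month 1 carries the same weight in the denominator as one treated for four years. The percentage then answers how many of those who started had the event while they happened to be observed. The objective asks what happens with long-term treatment.

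The gap matters most for risks that the protocol itself treats as late: Protocol 8.2 raises malignancy mainly as a long-term concern and sets up cardiac monitoring throughout. With 22 patients, a low crude percentage or a zero for such an event can read as reassurance when much of the planned observation time was never accrued.

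Period 2 has a related denominator problem. Under Protocol 5.2.5, a patient who enters ABX464-108 has the last visit at Month 48, one day after the last dose, and only those who do not enter return for the visit four weeks later. Patients who roll over have almost no Period 2 time in this study, yet the shell counts them fully in its denominator.

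**Working it through.** The plan has no figure to reproduce: sample size is not applicable in both documents, and no AE rate is stated.

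**Inputs from the documents**
- Enrolled: 15 + 7 = 22 (Protocol 1.3).
- Not in the Month 12 set: 3, so 22 − 3 = 19 remained.
- Beyond 3 years: 14 (Protocol 1.2.5), so 19 − 14 = 5 others passed Month 12 but not 3 years at that date.
- Full follow-up: 22 × 4 = 88 patient-years.

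**Assumptions (not documented)**
- The 14 long-term patients: 3 to 4 years each.
- The 5 others: 1 to 3 years each. Protocol 5.3.1 says all ongoing patients had passed Month 36, so most or all of these have probably left.
- The three early leavers: about 1, 4 and 6 months. The 6 months is for the patient lost to follow-up.

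**Exposure**
- Early leavers: (1 + 4 + 6)/12 = 0.92 patient-years.
- Low: 14 × 3 + 5 × 1 + 0.92 = 47.9, which is 54% of 88.
- High: 14 × 4 + 5 × 3 + 0.92 = 71.9, which is 82% of 88.

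**Expected crude percentage, constant hazard of 10 per 100 patient-years**

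The formula is the mean over patients of 1 − exp(−0.10 t), with t in years. The terms are 0.0083 (1 month), 0.0328 (4 months), 0.0488 (6 months), 0.0952 (1 year), 0.2592 (3 years) and 0.3297 (4 years). The early leavers add 0.0899 in all.
- Low: (14 × 0.2592 + 5 × 0.0952 + 0.0899)/22 = 19.1%.
- High: (14 × 0.3297 + 5 × 0.2592 + 0.0899)/22 = 27.3%.
- All followed for 48 months: 1 − exp(−0.4) = 33.0%.

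**Dependence on onset**
- Late: suppose the event can arise only after Month 12, with a 20% risk by Month 48. A patient followed for 3 years has risk 1 − 0.8^(24/36) = 0.138. Low: 14 × 0.138/22 = 8.8%. High: (14 × 0.20 + 5 × 0.138)/22 = 15.9%. Both compare with 20%.
- Early: if the event is confined to the first month, all 22 patients are observed for essentially the whole risk window, and there is almost no shortfall.

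**What a rate would add**

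Four patients with one event each are 4/22 = 18.2% crude. As a rate they are 4/71.9 to 4/47.9, or 5.6 to 8.3 events per 100 patient-years.

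**Period 2**

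At most 22 × 28 days = 616 days, about 1.7 patient-years, and less for every patient who rolls over. One event would be 59 per 100 patient-years, with an exact 95% interval of 1.5 to 330. A rate is of little use here, but the number of patients followed is. SAP 5.1 exposure cannot supply Period 2 time, because it stops at the last dose.

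**The case against.** The strongest reply is that this is a 22-patient, open-label, purely descriptive extension. No test or error rate is affected. The primary endpoint is a count, which the SAP reports as E, whereas the shortfall calculated above concerns n (%). A reader can already get an overall on-treatment rate by dividing Period 1 events by n × mean exposure from Table 14.3.7. The illustrated gap of about 6 to 14 percentage points is also small beside sampling error: 5/22 has an exact 95% interval of 8% to 45%.

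All of that is true, and it limits the weight of the point. It does not remove it. E also depends on how long patients were followed. The hand calculation gives only one overall event rate; time to first event could be recovered only from the listings. Wide intervals are a reason to print them.

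A second reply is that a single rate assumes a constant hazard. Protocol 1.2.5 describes gastrointestinal symptoms and headache as occurring after treatment onset, and spreading such events over four years would understate the early risk. This stands, and it is why the crude n (%) should stay beside the rate.

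Readers might also infer more than the documents support:
- That long-term safety as a whole is reported without regard to time. It is not: laboratory values, vital signs, physical examination and ECG are summarised by visit (SAP 11.6.2 to 11.6.5). The gap is in the AE tables.
- That Periods 1 and 2 are set side by side for comparison. The programming notes put each period in its own display, with the period number in the header.
- That the two induction groups are distorted relative to each other. Losses before Month 12 were 2/15 (13%) and 1/7 (14%), so no such distortion is shown.

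**Conclusion.** The point holds for the AE tables. They relate no AE to time at risk, although the objective is long-term safety and on-treatment follow-up runs from about 1 to 48 months. Crude percentages fall below the 48-month risk for late-onset events and are close to right for early ones; a general claim that they understate AE risk would go too far.

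On the assumed follow-up, observed exposure is roughly 54% to 82% of the full 88 patient-years. The illustrated shortfall is 19% to 27% against 33%. These figures rest on undocumented leaving times for six patients, on the final follow-up of the 14 (documented only as beyond 3 years), and on an assumed constant hazard. They show the scale and are not a forecast. The remedy improves how the primary objective is described; it does not correct an invalid analysis.

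**What to change.** **Period 1.** In the tables of TEAEs, serious TEAEs, TEAEs leading to discontinuation and TEAEs of special interest, add patient-years at risk and events per 100 patient-years with 95% confidence intervals, by induction group and in total. SAP 5.1 exposure runs from first to last dose, so it matches Period 1. For events of special interest, also give first events per 100 patient-years, with each patient's time censored at the first event. State how the interval treats repeat events in one patient. Keep the crude n (%), and add a footnote that a single rate assumes a constant hazard. Identify the tables by title: SAP 11.6.1 and the table list in SAP 14.1 swap numbers 14.3.1.7 and 14.3.1.8 for the serious and severe tables.

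**Period 2.** Do not use SAP 5.1 exposure. State how many patients were actually followed after the last dose, and use that number as the percentage denominator.

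**Cost.** Low. Period 1 needs a few extra columns from dose dates and AE onset dates that are already listed; Period 2 needs one new derivation of who was followed. The tables become slightly longer, and with 22 patients the intervals will be wide. The SAP was written while treatment was ongoing, so the change could be made by amendment before database lock.
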